7.10.3 Clinical laboratory

Haematology, biochemistry and urinalysis are collected at the baseline and end-of-study visits only. For the purpose of summary tables on laboratory test results, any value reported as below the lower limit of quantification or as undetectable will be considered as missing, and any value reported as above the upper limit of quantification will be considered as being equal to the upper limit. In data listings, the reported value will be presented.

For continuous laboratory parameters, summary statistics on the laboratory test results will be presented by visit. For the end-of-study visit, summary statistics on the change from baseline will also be presented.

For categorical laboratory parameters, frequency tables on the laboratory test results will be presented by visit. For the end-of-study visits, the shift from baseline will also be presented.

For all laboratory parameters, frequency tables on the clinical interpretation of the laboratory test results (*e.g.* normal, abnormal but not clinically significant, abnormal and clinically significant) will be presented by visit. For the end-of-study visit, the shift from baseline will also be presented.

Each parameter will be presented in a separate table. A list of all laboratory parameters (including specification of the standardised units to be used for analysis) is presented below:

LINK Medical Study ID: PSR012

Clinical laboratory tests will be presented with summary statistics. In addition, the tests will be analysed with ANCOVA (baseline value of respective laboratory test will be included in the model).

All results will be regarded as descriptive only. The p-values will be used to flag safety and tolerability variables worthy of further attention.

Null hypothesis:

• No difference between test treatment and reference treatment

Clinical laboratory tests conducted at planned visits for which laboratory sampling was not planned, as well as unplanned visits with laboratory sampling that are reported through the eCRF, will be included in the listings and, if deemed necessary, commented in the Statistical report.

Laboratory class	Parameter*	Unit**
Haematology	Total red blood cell count	x10^12/L; x10^6/microlitre
	White blood cell count	x10^9/L; x10^3/microlitre; /microlitre
	Neutrophils	x10^9/L; %; /microlitre
	Lymphocytes	x10^9/L; %; /microlitre
	Monocytes	x10^9/L; %; /microlitre
	Eosinophils	x10^9/L; %; /microlitre
	Basophils	x10^9/L; %; /microlitre
	Haematocrit	L/L; %
	Haemoglobin	Mmol/L; mmolFe/L; g/dL; g/L
	Platelets	x10^9/L; x10^3/microlitre
Biochemistry	Serum creatinine	Micromol/L; mg/dL
	Aspartate aminotransferase	U/L
	Alanine aminotransferase	U/L
	Glucose	Mmol/L; mg/dL
	Serum sodium	Mmol/L; mEg/L
	Serum potassium	Mmol/L; mEg/L
	Total protein	g/L; g/dL
	Total bilirubin	Micromol/L; mg/dL
	Alkaline phosphatase	U/L
	Gamma-glutamyl transferase	U/L
	Cholesterol	Mmol/L; mg/dL
	Triglycerides	Mmol/L; mg/dL
	riigiyociides	Willow E, Migrat
Urinalysis	Specific gravity	
	рН	
	Protein	Positive/Negative
	Glucose	Positive/Negative
	Ketones	Positive/Negative
	Urobilinogen	Positive/Negative
	Erythrocytes	Positive/Negative

LINK Medical Study ID:	PSR012	
	Leucocytes	Positive/Negative

^{*}All measured values are coded as either NCS=Not clinically significant or CS=Clinically significant

Test results reported in other units will be converted from their original units to the standardised units specified in the table above before analysis, using appropriate conversion factors. Data listings will include test results in both SDTM, SI and original units, wherever they differ, by using the LBSCAT variable in SDTM.

7.10.4 **Vital Signs**

Diastolic and systolic blood pressure, pulse rate and body temperature are only measured at baseline, which will be presented in a table. These are annotated as ORRES DIABP, ORRES SYSBP, ORRES PULSE and ORRES TEMP.

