8.2 Demographics and Baseline Characteristics

Age and sex will be presented using counts, means and rates. Frequency of risk factors present at baseline will also be tabulated. Risk factor is defined as any use of at least one of the following drugs given before baseline with ATC5:

Topical antifungals: amphotericin, voriconazole, chlorhexidine 0.2%, natamycin

Oral antifungals: voriconazole, itraconazole, fluconazole

Topical antivirals: aciclovir, gangciclovir

Oral antivirals: aciclovir, famciclovir, valaciclovir

Topical antibiotics: chloramphenicol, moxifloxacin, levofloxacin, ofloxacin, gatifloxacin, gentamicin, neomycin

Topical steroid potent: dexamathasone 0.1% or Prednisolone forte 1%)

Topical steroid mild: prednisolone 0.5%, FML (fluromethalone), loteprednol

Diagnostic test criteria will be categorised into four (4) groups and be presented in a frequency table:

- Patients diagnosed by IVCM alone: variables CFMPERF and CFMORRES with value Yes
- Patients diagnosed by IVCM with culture: variables CFMPERF and CFMORRES with value Yes and CSORRES with value Positive
- Patients diagnosed by IVCM with PCR: variables CFMPERF and CFMORRES with value Yes and PCRORRES with value Positive
- Patients diagnosed by IVCM with PCR and culture: variables CFMPERF and CFMORRES with value Yes and CSORRES and CFMORRES with value Positive

Change from Baseline

LINK Medical Study ID: PSR012

Change from baseline will be computed as the difference between a post-baseline value and the corresponding baseline value.

Percentage change from baseline will be computed as 100 times the change from baseline divided by the baseline value.

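### Deleting laboratory values below the quantification limit raises visit means and tends to pull changes and arm differences toward zero; set them to the limit, as is done at the upper end

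*SAP*

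**What the plan says.** SAP section 7.10.3 sets the rule in one sentence. It opens "For the purpose of summary tables on laboratory test results" and then deals with the low end: "any value reported as below the lower limit of quantification or as undetectable will be considered as missing". The high end is handled differently, by substitution: "any value reported as above the upper limit of quantification will be considered as being equal to the upper limit". The section then adds: "In data listings, the reported value will be presented". No reason is given for treating the two ends differently.

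The same section limits the data to two time points: "Haematology, biochemistry and urinalysis are collected at the baseline and end-of-study visits only". For continuous parameters, "For the end-of-study visit, summary statistics on the change from baseline will also be presented". SAP section 8.2 defines that quantity: "Change from baseline will be computed as the difference between a post-baseline value and the corresponding baseline value". A subject therefore needs both values to contribute.

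Section 7.10.3 also plans an ANCOVA of the laboratory tests adjusted for the baseline value, with p-values used only to flag variables for further attention. It does not say whether the quantification-limit rule carries over to that model. SAP section 7.1.1 asks for the number of missing observations in each continuous summary. No separate count of values outside the limits is planned.

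**The concern.** A result below the quantification limit is not unknown; it is known to lie in the low tail. Treating it as missing removes values because they are low, so the missingness is informative by construction. Above the upper limit the plan keeps the subject and records the limit, so it already accepts substitution at one end.

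Three things are at stake, all of them in safety tables:

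- Visit means for affected parameters are computed on the upper part of the distribution only.
- A subject who moves from measurable to below the limit, or the reverse, drops out of the change summary. That subject may be the one with the largest change.
- Under section 7.1.1 the deleted results are counted together with tests never done, so the table cannot show that a low result was obtained.

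The word undetectable is also not restricted to continuous tests. Most urinalysis items in section 7.10.3 are recorded as positive or negative. Read literally, the rule could turn a negative dipstick into a missing one.

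**Working it through.** The documents give no assay limits, no share of values outside them and no standard deviations, so there is no plan figure to reproduce. All inputs below are assumptions, shown as ranges.

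**1. A simple scale example.** Assume a limit of 0.1 and a mean of 0.15 among quantified values. With a share p below the limit, the planned mean is 0.150 for every p, because the low values are dropped. The limit-substituted mean is (1 − p) × 0.15 + p × 0.10.

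| p | Substituted mean | 0.150 / substituted |
|---|---|---|
| 5% | 0.1475 | 1.017 |
| 10% | 0.1450 | 1.034 |
| 20% | 0.1400 | 1.071 |
| 30% | 0.1350 | 1.111 |

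The comparison is with the substituted mean, not the true mean. The true mean is lower still, because every deleted value lies below 0.1.

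**2. Visit mean in SD units, none above the upper limit.** Assume standard normal values, with a = Φ⁻¹(p). Bias under deletion is φ(a)/(1 − p). Bias under substitution is φ(a) + a·p. At 10%: a = −1.2816 and φ(a) = 0.1755, giving 0.1755/0.90 = 0.195 and 0.1755 − 0.1282 = 0.047.

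| Share below | Deletion (plan) | Substitution | Bias removed |
|---|---|---|---|
| 5% | +0.109 | +0.021 | 81% |
| 10% | +0.195 | +0.047 | 76% |
| 20% | +0.350 | +0.112 | 68% |

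The last column is 1 − substitution/deletion.

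**3. Adding the upper-limit rule.** With b = Φ⁻¹(1 − q) for a share q above the upper limit, the bias is [φ(a) − φ(b) + b·q]/(1 − p). Capping alone lowers the mean, by 0.021, 0.047 and 0.112 SD at q = 5%, 10% and 20%. The net bias is +0.087 SD at 5% below and 5% above, +0.006 at 1% below and 5% above, −0.021 at 1% below and 10% above, and −0.009 at 5% below and 20% above. It is upward unless high-end censoring dominates.

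**4. Mean change.** Simulation used 4,000,000 baseline and end-of-study pairs per scenario, correlation 0.5, none above the upper limit, and the share below the limit fixed at baseline. Bias of the mean change, in SD:

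| True change | 5% below | 10% below | 20% below |
|---|---|---|---|
| −0.5 | +0.069 | +0.102 | +0.146 |
| 0 | +0.002 | −0.001 | 0.000 |
| +0.5 | −0.035 | −0.058 | −0.097 |

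Across correlations 0.3 to 0.7, the bias for a true fall runs from +0.046 to +0.185 and for a true rise from −0.022 to −0.125. Adding 5% above the upper limit leaves these signs unchanged. The pull is toward zero in both directions. A lost low end-of-study value removes a fall; a lost low baseline value removes a likely rise.

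**5. Arm difference in change.** Let one arm fall by 0.5 SD and the other stay unchanged, with correlation 0.5. The true difference of −0.5 is estimated as −0.431, −0.399 and −0.355 at 5%, 10% and 20% below the limit. That is a shrinkage of 14%, 20% and 29% (1 − 0.431/0.5, and so on).

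**The case against.** The strongest reply is that little depends on these tables. Laboratory data are collected at two visits and all laboratory results are declared descriptive. Listings show the reported value. Section 7.10.3 plans frequency tables of clinical interpretation for every parameter, with shift from baseline at end of study. Protocol section 6.1.6 requires clinically significant abnormal values to be recorded as adverse events. All of this stands, and it keeps the point minor. It does not correct the means and changes that the SAP still plans to print.

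A reader might infer four stronger things, none of which the documents support:

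- *Changes are biased upward.* They are not, as a general matter. With no true change the losses at the two visits cancel; otherwise the change shrinks toward zero.
- *Both halves of the rule push means up.* Capping at the upper limit pushes them down and can reverse the net bias.
- *The ANCOVA p-values are distorted.* The rule is written for summary tables only. Whether the ANCOVA uses it is unstated, so this is a point to clarify and not an established fault.
- *Real falls are hidden.* A clinically relevant fall can still appear in the listings, the shift tables and the adverse event record. What is weakened is the mean change as a signal.

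The dipstick concern is likewise one reading of loose wording. Because section 7.1.1 keeps subjects with missing data in the denominator, the percentage positive would not change. Only negatives and shifts would be undercounted.

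**Conclusion.** The rule deletes results known to be low, and the plan gives no reason for handling the two ends differently. For affected continuous parameters, visit means are biased upward unless values above the upper limit are much more common than values below the lower one. Mean changes and arm differences are typically attenuated.

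The real size cannot be known from the documents, because it depends on a share of below-limit values that they do not give. If that share is near zero for a parameter, so is the bias. The percentages rest on the assumed limit of 0.1 and quantified mean of 0.15. The SD figures rest on normal values, whereas parameters that sit near a floor are often skewed, so they show direction and order of magnitude only.

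This is a low-priority improvement to a descriptive safety analysis. It has no bearing on the primary efficacy conclusion.

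**What to change.** Amend SAP section 7.10.3 as follows:

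- For continuous parameters, set values below the lower limit of quantification, or undetectable, equal to that limit, mirroring the existing upper-limit rule.
- Count undetectable dipstick results as negative, not missing.
- State that the same handling applies in the ANCOVA.
- Report the number of values below the lower and above the upper limit, by arm and visit, separately from tests not done.

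The cost is a few sentences and one extra count per table, with no new measurements. Testing is done at local laboratories (Protocol section 6.1.6), so the limit to use is the one that applies to each reported result. Where a laboratory reports only that nothing was detected, its limit has to be obtained.

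The downside is a small residual upward bias in visit means: +0.021, +0.047 and +0.112 SD at 5%, 10% and 20% below the limit, against +0.109, +0.195 and +0.350 SD under deletion. Substitution still understates a fall that ends below the limit, but the subject stays in the change summary and is counted.

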7.10.5 Intraocular Pressure Measurement (mmHg)

IOP is measured at all visits as integer numbers with unit mmHg. The annotation is IOPRES.

7.10.6 **Ophthalmoscopy**

Ophthalmoscopic assessments are conducted for the vitreous, retina, macula and choroid. Clinically significant findings, reported as Abnormal, CS, are to be recorded in the AE log. The annotations are ORRES VIT, ORRES RET, ORRES MAC and ORRES CHD. The tables can be seen in the DDP.

7.10.7 Worsening of corneal inflammation

This is defined as development of ring abscess and/or hypopyon despite >30 days of treatment with the study drug. The table is presented in the DDP.

Rate of subjects with a relapse 7.10.8

The rate of subjects with relapse will be tabulated, see the DDP. Relapse is recorded in the annotated variable RELAPSYN.

7.10.9 Rate of subjects requiring surgery

Rate of subjects requiring surgery, including amniotic membrane transplants, superficial keratectomy, application of cyanoacrylate glue, therapeutic penetrating, lamellar keratoplasty, cataract surgery, evisceration, or enucleation, will be tabulated, see the DDP. Such surgery will be seen in the annotated variable CMTRT, Name of (prior or concomitant) drug/medication/therapy.

7.10.10 Rate of subjects requiring non-study therapies

Rate of subjects requiring non-study therapies will be tabulated or listed, see DDP. The annotated variable CMTRT will be used as basis.

7.10.11 Rate of subjects' discontinuation from study

The rate of subjects discontinuing the study will be presented, see the DDP. The annotated variable DSCOMP with values Yes/No as answer to the question "Did the subject complete the study as per protocol?" will be used. The primary reason for study discontinuation, annotated variable DSDECOD, will also be presented.

The rate of subjects discontinuing the treatment will be presented in a similar fashion, using the DSTRTYN annotated variable, which answers the question "Did the subject complete the treatment as per protocol?". The primary reason for discontinuation, annotated variable DSDECOD, will also be presented. The primary reason for treatment discontinuation, annotated variable DSDECOD TRT, will also be presented.

7.10.12 Incidence of secondary complication

Incidence of secondary complications, such as significant corneal neovascularization, corneal scarring, corneal perforation, scleritis, secondary glaucoma, cataract, retinopathy will be presented, see the DDP. Such complications will be retrieved from the AE data.

^{**} The results of the analyses and data presented in tables will be in SI units.

LINK Medical Study ID:

PSR012

7.10.13 Cure rate of subjects with risk factor

The cure rate of subjects with risk factor defined in section 8.2 will be presented in a frequency table.

7.10.14 Rate of subjects with Adjunctive therapy

The rate of subjects that need Adjunctive therapy will be presented in a frequency table.

Adjunctive therapy is defined as new use after baseline or any increase of at least one of following medication with ATC5:

Topical steroid: dexamethasone, prednisolone, fluorometholone, loteprednol

Oral non-steroidal anti-inflammatories (NSAIDS): diclofenac, ibuprofen, flurbiprofen, naproxen

7.11 Changes to Planned Analysis

At this time, no changes to the planned analyses are being considered.

However, the definition of the PPAS have been altered compared to the protocol due to one wrong sentence.

The use of normal-distribution test assumptions will be the primary choice. If such assumptions should be found incorrect during the analysis of the data, an assessment of which type of analysis that should be used, will be conducted. This will be described in detail in the clinical study report.

8 Derived Variables

8.1 Disposition of Subjects

A screening failure is defined as a screened but not randomised subject.

8.2 Demographics and Baseline Characteristics

Age and sex will be presented using counts, means and rates. Frequency of risk factors present at baseline will also be tabulated. Risk factor is defined as any use of at least one of the following drugs given before baseline with ATC5:

Topical antifungals: amphotericin, voriconazole, chlorhexidine 0.2%, natamycin

Oral antifungals: voriconazole, itraconazole, fluconazole

Topical antivirals: aciclovir, gangciclovir

Oral antivirals: aciclovir, famciclovir, valaciclovir

Topical antibiotics: chloramphenicol, moxifloxacin, levofloxacin, ofloxacin, gatifloxacin, gentamicin, neomycin

Topical steroid potent: dexamathasone 0.1% or Prednisolone forte 1%)

Topical steroid mild: prednisolone 0.5%, FML (fluromethalone), loteprednol

Diagnostic test criteria will be categorised into four (4) groups and be presented in a frequency table:

- Patients diagnosed by IVCM alone: variables CFMPERF and CFMORRES with value Yes
- Patients diagnosed by IVCM with culture: variables CFMPERF and CFMORRES with value Yes and CSORRES with value Positive
- Patients diagnosed by IVCM with PCR: variables CFMPERF and CFMORRES with value Yes and PCRORRES with value Positive
- Patients diagnosed by IVCM with PCR and culture: variables CFMPERF and CFMORRES with value Yes and CSORRES and CFMORRES with value Positive

Change from Baseline

LINK Medical Study ID: PSR012

Change from baseline will be computed as the difference between a post-baseline value and the corresponding baseline value.

Percentage change from baseline will be computed as 100 times the change from baseline divided by the baseline value.

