All subjects at screening meeting the inclusion criteria and including those with negative confocal microscopy findings will have corneal scrapes for culture and histology of *Acanthamoeba*, and to perform *Acanthamoeba* deoxyribonucleic acid (DNA) identification by polymerase chain reaction (PCR).

Note: this is being done for study quality, for correlation with confocal microscopy findings, and to identify patients with fungal and viral infection. Because culturing and PCR will take 2 to 8 days, during which time subjects thought clinically to have *Acanthamoeba* keratitis would be starting treatment before randomization, this assessment is not part of the inclusion criteria. Subjects who have been proven to have fungal and viral infections, if randomized on the basis of clinical and confocal microscope findings, will be removed from the study, even though they may have concomitant *Acanthamoeba* keratitis.

Subjects with a negative confocal microscopy evaluation, but a positive PCR/Culture (confocal false negative) will not be enrolled in the study but will be treated with the best clinically available treatment outside the study.

Subjects meeting the inclusion criteria, including findings on slit lamp examination and confocal microscopy consistent with Acanthamoeba keratitis are entered into the study and randomized to one of the two treatment arms. They will then enter the Treatment Plan and Follow-up protocol as presented in figure 2: Schematic Presentation of the Treatment and Follow-up Protocol as presented in 5.3.

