4.1. Inclusion Criteria

Each potential subject must satisfy all of the following criteria to be enrolled in the study:

- 1. Subject must be able and willing to give informed consent.
- 2. Subject must be a man or woman of any race and ≥12 years of age, inclusive. Subjects <18 years will only be enrolled in selected study sites.
- 3. Subject must be able to understand and willing to comply with study procedures, restrictions and requirements, as judged by the investigator.
- 4. Clinical findings consistent with *Acanthamoeba* keratitis.

Clinical findings include the following:

- Epithelial lesions: epithelial punctate keratopathy, epithelial infiltrates, epithelial defects, dendritiform epithelial ulcers.
- Extracorneal lesions: limbal inflammation (limbitis), anterior scleral inflammation, diffuse or nodular.
- Stromal lesions: perineural infiltrates, anterior stromal infiltrates, disciform corneal swelling, stromal ulceration, ring abscess.
- Anterior chamber lesions: keratic precipitates, hypopyon.
- Late findings: fixed dilated pupil, mature cataract.
- 5. Confocal microscopy findings consistent with *Acanthamoeba* keratitis (performed within 7 days prior to study entry or as part of screening procedures)
 - Confocal microscopy findings include: cysts are round or ovoid, may show a double wall and are 15-30 µm in size.
- 6. Subjects using the following previous treatments for Acanthamoeba keratitis are eligible for the study:

Antibiotics: subjects who have an ocular bacterial infection at baseline are eligible
for the study. However, only topical moxifloxacin is permitted, unless resistant or
contraindicated.

Note: subjects who develop intercurrent bacterial infections will be retained in the study and treated with topical moxifloxacin.

• Antiviral drugs and antifungal drugs: subjects are often misdiagnosed as having these infections when they have *Acanthamoeba* keratitis. Subjects taking antivirals and antifungal agents (except for any using PHMB or Chlorhexidine) for a misdiagnosis can be included, but must discontinue these drugs after entry into the study.

Note: subjects who are thought to have combined *Acanthamoeba* keratitis with herpes or fungal keratitis are excluded from the study.

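### The SAP 8.2 rule for diagnosis by confocal, PCR and culture names the confocal variable twice and omits PCR, and the four diagnostic groups overlap as written

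*SAP*

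**What the plan says.** SAP section 8.2 states: "Diagnostic test criteria will be categorised into four (4) groups and be presented in a frequency table". The four rules follow:

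- Rule 1: "Patients diagnosed by IVCM alone: variables CFMPERF and CFMORRES with value Yes"
- Rule 2: "Patients diagnosed by IVCM with culture: variables CFMPERF and CFMORRES with value Yes and CSORRES with value Positive"
- Rule 3: "Patients diagnosed by IVCM with PCR: variables CFMPERF and CFMORRES with value Yes and PCRORRES with value Positive"
- Rule 4: "Patients diagnosed by IVCM with PCR and culture: variables CFMPERF and CFMORRES with value Yes and CSORRES and CFMORRES with value Positive"

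The words at issue in rule 4 are its closing condition, "CSORRES and CFMORRES with value Positive".

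Neither document gives a hierarchy among the rules or says that a subject is counted only once. SAP section 7.1.1 places mock tables in a separate Data Display Plan, which is not among the documents.

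Consistent confocal findings are an entry requirement (protocol section 4.1, criterion 5). Subjects who are confocal-negative but PCR- or culture-positive are not enrolled (protocol section 3.1.2). Culture and PCR are not entry criteria; the same section says they serve study quality, correlation with the confocal findings, and detection of fungal and viral infection.

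**The concern.** The label of rule 4 promises subjects positive on all three tests, but its conditions never look at PCR. Rule 3, one line above, shows that PCRORRES is the PCR variable. The label of rule 1 says alone, but its conditions do not look at culture or PCR at all.

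At stake is whether the table can show how many confocal diagnoses were supported by culture, by PCR, by both, or by neither. Readers will want this, because entry rests on the investigator's confocal reading: images go to a central reader, but the investigator's decision is accepted for inclusion (protocol section 6.1.2).

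**Working it through.** The plan states no figure on this point, so the check is one of logic. Take a subject with CFMPERF = Yes and CFMORRES = Yes and apply the rules to each combination of culture and PCR in three ways:

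- **Literal:** CFMORRES in rule 4 must be Yes and Positive at once.
- **Lenient:** Positive is taken as Yes for CFMORRES. Dropping the repeated condition gives the same result.
- **Corrected:** PCRORRES is used in rule 4, and rules 1 to 3 carry exclusions.

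| Culture | PCR | Literal: rules met | Lenient: rules met | Corrected: rule met |
|---|---|---|---|---|
| not positive | not positive | 1 | 1 | 1 |
| not positive | positive | 1, 3 | 1, 3 | 3 |
| positive | not positive | 1, 2 | 1, 2, 4 | 2 |
| positive | positive | 1, 2, 3 | 1, 2, 3, 4 | 4 |

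Three results do not depend on any positivity rate:

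1. Rule 4 is never met on the literal reading. On the lenient reading it is identical to rule 2, so culture-positive, PCR-negative subjects are reported as confirmed by both tests.
2. Rule 1 is met in every row on both readings.
3. Rules 2 and 3 overlap, because a subject positive on both tests meets each. Correcting rules 1 and 4 alone would not make the groups exclusive.

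**Illustration of scale.** N = 130 is the planned sample size (SAP section 5.1). The rest is assumed: all subjects have CFMPERF and CFMORRES = Yes, culture is positive with probability c, PCR is positive with probability p, and the two are independent. Counts for rules 1/2/3/4 are:

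- Literal: N, Nc, Np, 0; sum N(1 + c + p).
- Lenient: N, Nc, Np, Nc; sum N(1 + 2c + p).
- Corrected: N(1−c)(1−p), Nc(1−p), Np(1−c), Ncp; sum N.

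| c, p | Literal (sum) | Lenient (sum) | Corrected (sum) |
|---|---|---|---|
| 30%, 50% | 130/39/65/0 (234) | 130/39/65/39 (273) | 45.5/19.5/45.5/19.5 (130) |
| 50%, 70% | 130/65/91/0 (286) | 130/65/91/65 (351) | 19.5/19.5/45.5/45.5 (130) |
| 60%, 80% | 130/78/104/0 (312) | 130/78/104/78 (390) | 10.4/15.6/41.6/62.4 (130) |

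**Can a reader recover the missing count?** No. In the middle literal row, the number positive on both tests is only bounded, between 65 + 91 − 130 = 26 and the smaller of 65 and 91, which is 65. If rule 4 alone were corrected, the exclusive groups could be recovered by subtraction: 130 − 65 − 91 + 45.5 = 19.5 for alone. The error in rule 4 therefore loses information; the overlap mislabels it.

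**The case against.** The strongest reply is that the labels make the intent plain. A separate combined group implies that rules 2 and 3 mean one test only, alone implies no positive culture or PCR, and the PCR variable is named one line above the slip. A programmer would probably notice a group that is empty by construction, and the Data Display Plan may show the intended layout. This stands as a limit: the table would be wrong if programmed as written, and it does not follow that it will be. It does not remove the point, because the written conditions contradict the labels and no stated rule resolves them. The missing exclusions are also easier to overlook than the repeated variable.

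A reader might infer more than the documents support:

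- **That rule 4 gives zero whatever the data.** This holds only on the literal reading; the lenient one duplicates rule 2.
- **That the alone group is 100% of those enrolled.** Rule 1 also needs CFMPERF = Yes. Confocal microscopy is optional at screening if done in standard care within the previous 7 days (note 8 to the Schedule of Assessments), and the documents do not say how CFMPERF is coded for those subjects.
- **That the error undermines the Full Analysis Set.** SAP section 7.2.1 requires a confirmed diagnosis but does not refer to these groups, and section 7.2 leaves the classification of subjects to the clean file meeting. What counts as confirmed is a separate question, which correcting this table would not settle.

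**Conclusion.** The point holds as an error in a derivation rule. Rule 4 omits PCR, and as written its group is either empty or a copy of the culture group. Rules 1 to 3 carry no exclusions, so the four groups overlap, contrary to their labels. The alone group takes in every subject with CFMPERF and CFMORRES equal to Yes.

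The consequence is small: one descriptive baseline table. The primary analysis, the significance level and the sample size are unaffected. The logical results rest only on the text of SAP section 8.2. The illustrative counts rest on the assumed positivity rates, independence of the two tests, and CFMPERF and CFMORRES equal to Yes for all 130 subjects.

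**What to change.** In SAP section 8.2, keep CFMPERF and CFMORRES = Yes throughout and amend the rest:

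- Rule 1: add CSORRES not Positive and PCRORRES not Positive.
- Rule 2: add PCRORRES not Positive.
- Rule 3: add CSORRES not Positive.
- Rule 4: replace the second CFMORRES with PCRORRES.

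Not Positive on its own would pool negative results with tests that are missing or were not done. Corneal scraping is optional at screening if already done in standard care within the previous 7 days (note 9 to the Schedule of Assessments), so results may not be recorded for everyone in the same way. The table should therefore show tests missing or not done separately from negative results.

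The cost is four edited lines and one sentence on missing tests, with the Data Display Plan checked to match. No new data are needed and no other analysis changes.
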